### 5.1 Participant Inclusion Criteria

In order to be eligible to participate in this study, an individual must meet ALL of the following criteria:

1. Signed and dated IRB-approved informed consent form (ICF).
2. Men or women between the ages of 18 and 60, inclusive.
3. Subjects in good health as determined by medical history, physical and focused neurological examinations, clinical laboratory studies, electrocardiograms (ECGs), vital signs, and Investigator's judgement.
4. Presence of bilaterally symmetrical GL of moderate to severe rating at maximum frown, as measured using FWS by both the Investigator and subject prior to study treatment.
5. Subjects with sufficient visual acuity without the use of eyeglasses (contact lens use acceptable) to accurately assess their facial wrinkles as determined by the Investigator's judgement.
6. Women of child bearing potential must not be pregnant, lactating, or planning to become pregnant during the study.
7. Women of non-childbearing potential must be either postmenopausal (at least 12 consecutive months of amenorrhea) or surgically sterile (e.g., tubal ligation, hysterectomy, etc.).

8. Women of childbearing potential agreeing to use dual methods of contraception from the day of dosing until 3 months afterwards. Female subjects using oral contraception must have initiated treatment at least 2 months prior to the day of dosing.
9. Male subjects with partner(s) of childbearing potential agreeing to use dual methods of contraception from the day of dosing until 3 months afterwards, and to no sperm donation from day of dosing until 3 months afterwards.
10. Willing and able to complete protocol requirements and instructions, which includes completion of all required visits.

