### **7.1.1.3 Assessment of Inclusion/Exclusion Criteria**

At the Screening and the Baseline (prior to dosing) Visits, the site staff will be responsible for reviewing the inclusion and exclusion criteria to determine the subject's eligibility for the study.

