#### **7.1.1.17 Pregnancy Test**

At the Screening Visit, blood samples for pregnancy test for women of child bearing potential will be collected. The samples will be analyzed by a central laboratory (with the appropriate accreditations or certifications).

At the Baseline (prior to dosing) Visit and Day 30 (EOS/ET) Visit, urine samples for pregnancy test for women of child bearing potential will be collected. The samples will be analyzed at the study site. Any positive findings at the Screening or Baseline Visit will exclude subject from participating in the study. See [Section 8.5.2](#) in the event of any positive findings during the study.

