#### **7.1.1.18 Study Drug Administration**

At the Baseline Visit, upon conducting all specified pre-dose assessment and confirming subjects remain eligible for the study, study drug will be administered. Six subjects in a cohort will be treated with either EB-001 or placebo in a ratio of 5:1 in a double-blind manner.

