## 7.3 Study Schedule

### 7.3.1 Screening Visit (Days -30 to -1)

Screening (Visit 1, Days -30 to -1, inclusive) will include the procedures and evaluations set forth in [Section 7.3.7](#).

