## 7.6 Subject Restriction

The following restrictions apply:

- Female of childbearing potential must agree to use dual methods of contraception from the day of dosing for 3 months. Female subjects using oral contraception must have initiated treatment at least 2 months prior to the day of dosing.

- Male subjects with partner(s) of childbearing potential must agree to use dual methods of contraception from the day of dosing for 3 months, and to no sperm donation from day of dosing until 3 months afterwards.
- Subjects must not donate blood or plasma from 30 days prior to Screening until the last follow-up visit (Day 42).
- Subjects should not consume more than moderate amount of alcohol per day (i.e., 1 drink per day for women or 2 drinks per day for men).

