### 8.5.2 Reporting of Pregnancy

Females that may be able to get pregnant will be required to take pregnancy test before study agent administration. The results of the pregnancy testing must be negative in order to be in the study.

All female subjects who may be able to get pregnant must agree to use dual methods of contraception from the day of dosing until 3 months afterwards. Female subjects using oral contraception must have initiated treatment at least 2 months prior to the day of dosing. All

male subjects with partner(s) of childbearing potential must agree to use dual methods of contraception from the day of dosing until 3 months afterwards, and to no sperm donation from day of dosing until 3 months afterwards.

In the event that a female subject does become pregnant at any time during the study, the Investigator must notify the Medical Monitor or designee within 48 hours of learning about the pregnancy.

The Investigator will be required to complete the Pregnancy Notification Form and any additional documents provided by the Sponsor, follow the subject through the pregnancy term, and report to the Medical Monitor or designee the course of the pregnancy, including perinatal or neonatal outcome.

Information on the status of the mother and the child will be forwarded to the Medical Monitor or designee using the Pregnancy Notification Follow-up Form. Any premature termination of the pregnancy will also be reported on this form.

Although pregnancy occurring in a clinical study is not considered to be an SAE, any pregnancy complication or elective termination of a pregnancy for medical reasons will be recorded as an AE and will be followed as such. A spontaneous abortion is considered to be an SAE.

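### Required contraception for women of childbearing potential starts only on the day of dosing; a 14-day lead-in would be a minor, cheap safety improvement

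*Combined protocol and SAP*

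**What the plan says.** **Contraception.** Section 5.1, criterion 8, reads "Women of childbearing potential agreeing to use dual methods of contraception from the day of dosing until 3 months afterwards", and the Protocol Summary repeats it. Section 7.6 says "Female of childbearing potential must agree to use dual methods of contraception from the day of dosing for 3 months". Section 8.5.2 says "All female subjects who may be able to get pregnant must agree to use dual methods of contraception from the day of dosing" and gives the same 3-month end point. All but one of these duties begin at dosing. The exception, found in all four places, is that a woman on oral contraception must have started it at least 2 months earlier.

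**Pregnancy status.** Criterion 6 states "Women of child bearing potential must not be pregnant, lactating, or planning to become pregnant during the study".

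**Testing.** Section 7.1.1.17 has a serum test at Screening, analysed centrally. It then adds "At the Baseline (prior to dosing) Visit and Day 30 (EOS/ET) Visit, urine samples for pregnancy test", analysed at the site. A positive result at Screening or Baseline excludes the woman.

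**Timing and eligibility review.** Section 7.3.1 sets the window: "Screening (Visit 1, Days -30 to -1, inclusive) will include the procedures". Section 7.1.1.3 says "At the Screening and the Baseline (prior to dosing) Visits, the site staff will be responsible for reviewing the inclusion and exclusion criteria" in order to determine eligibility.

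**After dosing.** Section 8.5.2 requires notification within 48 hours of the investigator learning of a pregnancy, and follow-up to its outcome.

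**The concern.** A pregnancy test cannot detect a conception until some days have passed. During that interval only contraception or abstinence protects against dosing a pregnant woman, and the plan requires neither before Day 0 unless she uses the pill. The treatment is a single first-in-human injection that cannot be withdrawn, so contraception begun that day does nothing for a conception already present.

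The sponsor plainly treats pregnancy after exposure as something to avoid: it asks for dual methods for 3 months after one dose. The 2-month rule for pill users also shows that it wants that method established by Day 0. Users of other methods have no equivalent rule. What is at stake is participant protection. The sample size, the descriptive analysis and the study's conclusions are not affected.

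**Working it through.** The protocol gives no figure on this point to reproduce, so the check is a comparison of sections plus simple day counts.

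**1. Does any section require cover before Day 0?**

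| Section | Required before Day 0 | What it leaves open |
|---|---|---|
| 5.1 criterion 8, Protocol Summary, 7.6, 8.5.2 | 2 months' prior use, pill users only | Women on other methods or none |
| 5.1 criterion 6 | Not pregnant, lactating or planning pregnancy | An unplanned conception not yet detected |
| 7.1.1.17 | Negative serum and urine tests | A conception inside the detection lag |
| 7.1.1.3 | Eligibility reviewed at Screening and Baseline | Prior contraception is not a criterion, except for the pill |

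No readable section closes the gap. Screening may fall as late as Day -1, in which case the two tests are one day apart and share nearly the same blind interval. If Screening is earlier, a conception after it can be caught before dosing only by the Baseline urine test.

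**2. How long is the exposed interval?** Let L be the detection lag, assumed to be 7 to 14 days. The pre-dose days on which a conception could go undetected at Baseline, with no cover required, are then 7 to 14 for a woman not on oral contraception. The argument needs only L > 0.

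**3. When is the next scheduled test?** Day 30 ± 2 days (7.3.4), that is Day 28 to Day 32, or the early termination visit if sooner. For a conception between Day -14 and Day 0, the time from conception to the Day 30 test runs from 28 - 0 = 28 days to 32 + 14 = 46 days.

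**4. Can a case count be computed?** No. It needs the number of women of childbearing potential without pre-dose cover and their chance of conceiving, and the documents give neither. To show how far the answer moves, suppose 10 such women, a conception chance c of 1% to 20% per 28-day cycle, and L of 7 to 14 days:

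- chance per woman q = c × L/28, from 0.01 × 7/28 = 0.0025 to 0.20 × 14/28 = 0.10
- expected cases 10q, from 0.025 to 1
- chance of at least one case 1 - (1 - q)^10, from about 2.5% to about 65%

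That span comes entirely from the assumptions and is not an estimate.

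**5. What delay would a 14-day lead-in cause?** For an uncovered woman screened on Day -s who begins cover that day, the delay is max(0, 14 - s) days:

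- s = 14 to 30 (17 of the 30 possible days): none
- s = 1 to 13 (the other 13 days): 13 days down to 1 day

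Dosing then falls 14 days after Screening, inside the 30-day window.

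**The case against.** The best case against the point is that this is a deliberate, uniform rule with reasonable safeguards around it. There are two pre-dose tests, planned pregnancy is barred, eligibility is re-checked before dosing, and any pregnancy is followed to its outcome. Section 6.1.9 counts the study's duration from the first screening visit, so criterion 6 arguably applies during screening too. The lag is an assumption and the benefit cannot be sized. Much of the nonclinical and risk text is redacted and may contain the sponsor's reasons for a Day 0 start. The consent form is not available and may already give pre-dose advice.

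Most of this stands, and it is why the point is minor. It does not remove the gap: criterion 6 concerns status and intention, and imposes no contraception before dosing.

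It could also be objected that an uncovered woman who starts the pill at Screening would miss the 30-day window altogether. That follows from the existing 2-month clause and is not a cost of the change.

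A reader might infer that dosing such a woman would be a protocol deviation under 14.3. The documents do not settle this. Section 8.5.2 frames eligibility as a negative test result, and a site that dosed after two negative tests would have followed every stated procedure.

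**Conclusion.** The point holds as a minor, optional safety improvement. On the readable text, a woman of childbearing potential not using oral contraception could conceive shortly before Day 0, test negative twice and be dosed. This rests on an assumed detection lag of about 7 to 14 days. The number of cases is probably very small: about 42 subjects of both sexes aged 18 to 60 are planned (at most 54), and women planning pregnancy are excluded. That is a judgement, since no count can be computed.

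Three stronger readings are not supported:

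- **An internal error.** The four statements of the rule agree with one another.
- **A demonstrated fetal hazard.** The visible text gives no basis for sizing one.
- **A quantified risk or benefit.** The 5:1 allocation says which treatment such a woman would probably receive, not how often the situation arises. Any percentage for the risk left after the change would only restate the assumed lag and contraceptive effectiveness.

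**What to change.** In the Protocol Summary, 5.1 criterion 8, 7.6 and 8.5.2 (and in the consent form if it does not already say so), add to the clause for women of childbearing potential:

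> must have used effective contraception, or have been abstinent, for at least 14 days before dosing

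This is in addition to the existing dual-method requirement from dosing to 3 months. Keep the 2-month oral-contraceptive clause and the male clause unchanged. The sponsor's medical staff should confirm the 14 days and list the acceptable methods. Site staff ask one question at the Baseline review already planned in 7.1.1.3. A woman covered for 14 days qualifies at once, even if screened on Day -1.

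**Cost.** A protocol amendment with sponsor, investigator and IRB approval before use (13.6), and text changes in four places. No test is added. An uncovered woman screened between Day -13 and Day -1 waits 1 to 13 days. Because cohorts are sequential and reviewed before escalation (10.6.1, 8.7), this could slightly slow a cohort unless another eligible subject takes the place.

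**Limits.** The check relies on self-report, methods can fail, and a lag longer than 14 days would leave some days uncovered.

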## 5.2 Participant Exclusion Criteria

An individual who meets ANY of the following criteria will be excluded from participation in this study:

1. Any condition that precludes a subject's ability to comply with study requirements, including completion of the study visits or inability to read, understand, and/or self-assess GL severity using FWS.
2. Any uncontrolled systemic disease or other medical condition.
3. Any medical condition that may put the subject at increased risk with exposure to botulinum toxin of any serotype, including diagnosed myasthenia gravis, Eaton-Lambert syndrome, amyotrophic lateral sclerosis, or any other condition that might interfere with neuromuscular function.
4. Current or previous botulinum toxin treatment of any serotype.
5. Anticipated need for treatment with botulinum toxin of any serotype for any reason during the study (other than study treatment).
6. Known immunization or hypersensitivity to any botulinum toxin serotype.
7. Known allergy or sensitivity to any of the components of the study treatments, or any materials used in the study procedures.
8. Any of the following procedures or treatments occurring within the specified period prior to screening:
  - 3 months: Non-ablative resurfacing laser or light treatment, microdermabrasion, or superficial peels.
  - 6 months: Any facial cosmetic procedure with medium depth to deep facial chemical peels (e.g., trichloroacetic acid [TCA] and phenol), or mid facial or periorbital laser skin resurfacing.
  - 6 months: On topical retinoid therapy and/or topical hormone cream applied to the face, who have not been on a consistent dose regimen and are unable to maintain the same regimen for the study.
  - 12 months: Mid-facial or periorbital treatment with non-permanent soft tissue fillers.
  - 12 months: On oral retinoid therapy.
9. Prior periorbital surgery, facial lift (full face or mid face), brow lift, or related procedures (e.g., eyelid [blepharoplasty] and/or eyebrow surgery).

10. Prior mid face or periorbital treatment with permanent soft tissue fillers, synthetic implantation (e.g., Gore-Tex®), and/or autologous fat transplantation.
11. Marked facial asymmetry, dermatochalasis, deep dermal scarring, and/or excessively thick sebaceous skin.
12. The inability to substantially lessen facial rhytides (fixed lines) even by physically spreading them apart, as determined by the Investigator.
13. Permanent make-up that would interfere with the assessment of facial wrinkles.
14. Subjects who, in the Investigator's opinion, are unable or unwilling to maintain their standardized skin care regimen throughout the study period.
15. Any eyebrow or eyelid ptosis at baseline as determined by the Investigator.
16. Infection or skin disorder at the injection sites.
17. History of facial nerve palsy.
18. Recent history (within 6 months of screening) of alcohol or drug abuse based on the Investigator's judgement.
19. Anticipated need for surgery or overnight hospitalization during the study.
20. Current enrollment in an investigational drug or device study or participation in such a study within 30 days or 5 half-lives of the drug, whichever is longer, of entry into this study.

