### 3 OBJECTIVES AND PURPOSE

This will be the FIH study of EB-001 to evaluate safety and efficacy in GL.

The safety objective is whether a single treatment cycle of EB-001 IM injections into the glabellar muscles (procerus and bilateral corrugator muscles) has an acceptable safety, and tolerability profile at the tested dose range.

The efficacy objection is whether a single treatment cycle of EB-001 IM injections, at one or more of the tested doses, is more effective than placebo in the treatment of GL assessed using the FWS.

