#### Dosage:

[figure not shown]
Subjects in each cohort will be randomized to receive either EB-001 or placebo, and each cohort will receive a different dose level of EB-001, which will generally be at a higher dose than the previous cohort, although dose modifications may be made depending on the safety and tolerability.

The total dose will be the specified amount of EB-001, or placebo, divided into 5 injections; 1 injection into procerus at midline and a single injection into each of the medial and lateral corrugators bilaterally (Figure 1). Each subject will always receive 5 injections and the volume injected per site will be 0.1 mL. The spacing of injections into the lateral corrugators should be at or about 1 centimeter above the supraorbital ridge, which is known to minimize potential ptosis.

There is no diet or water restriction throughout the study.

Figure 1 Injection Sites

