#### 4.2.2 Primary Efficacy Endpoint

- The primary endpoint is the Investigator's assessment of GL severity at maximum frown using the FWS.

The FWS is a four-point scale that indicates severity of GL as follows: 0 = none, 1 = mild, 2 = moderate, or 3 = severe (see [Appendix 2](#) for sample FWS assessment sheet).

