## 7.5 Prohibited Medications, Treatments, and Procedures

During the study, subjects may not use the following medications, or have following treatments/procedures performed until after the EOS Visit.

- Any topical retinoid therapy or topical hormone cream applied to the face unless they have been on a consistent dose regimen and maintained the same regimen for at least 6 months before enrollment.
- Any oral retinoid drugs within 12 months of enrollment.
- Any drugs used for skin conditions within 3 months of enrollment.
- Any non-ablative resurfacing laser or light treatment, microdermabrasion, superficial peels within 3 months of enrollment.
- Any facial cosmetic procedure with medium depth to deep facial chemical peels (e.g., trichloroacetic acid [TCA] and phenol), or mid facial or periorbital laser skin resurfacing within 3 months of enrollment.
- Any mid-facial or periorbital treatment with non-permanent soft tissue fillers within 12 months of enrollment.
- Any history of botulinum neurotoxin treatment of any serotype.

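### The filler, implant, fat-graft and laser-resurfacing exclusions, and the on-study filler and laser-resurfacing prohibitions, name the mid-face and periorbital areas but not the glabella, which is the area injected and scored

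*Combined protocol and SAP*

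**What the plan says.** The treated area is the glabella: Section 4.1 (Dosage) specifies "1 injection into procerus at midline and a single injection into each of the medial and lateral corrugators bilaterally". The scored area is the same. Section 4.2.2 states: "The primary endpoint is the Investigator's assessment of GL severity at maximum frown using the FWS".

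Three items in Section 5.2, repeated in the synopsis, restrict earlier cosmetic procedures by facial area:

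- Exclusion 8, temporary fillers: "12 months: Mid-facial or periorbital treatment with non-permanent soft tissue fillers".
- Exclusion 8, second half of the first 6-month bullet: "or mid facial or periorbital laser skin resurfacing".
- Exclusion 10, with no time limit: "Prior mid face or periorbital treatment with permanent soft tissue fillers", and in the same item synthetic implants and fat grafts.

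Section 7.5, which applies until after the end-of-study visit, repeats the area limit for temporary fillers: "Any mid-facial or periorbital treatment with non-permanent soft tissue fillers within 12 months of enrollment". It does the same for laser skin resurfacing. It has no bullet for permanent fillers, implants or fat.

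**The concern.** None of these items names the glabella. Taken at its word, the plan excludes a subject who had temporary filler in the mid-face 11 months before screening, but not one who had it in the glabellar crease 1 month before. Glabellar filler placed on Day 10 is not on the prohibited list.

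Such a procedure acts on the line that the FWS rates and on the tissue around the injection sites. Filler placed during follow-up could look like a treatment response. Filler resorbing during follow-up could worsen the line and hide a response, or make placebo look worse than it is. The subject would not clearly count as a protocol deviation under Section 14.3. The subject would also stay in the analysis: the efficacy set in Section 10.3 keeps every randomized, dosed subject with one later efficacy assessment, and no per-protocol set is defined.

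**Working it through.** **Scope of the two lists.** The point rests on wording, so the items are set side by side.

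| Procedure | Section 5.2 | Section 7.5 | Glabella covered? |
|---|---|---|---|
| Temporary filler | Mid-face or periorbital, 12 months | Same sites, 12 months | Not named in either |
| Permanent filler, implant, fat | Mid-face or periorbital, ever | Not listed at any site | Not named in either |
| Laser skin resurfacing | Mid-face or periorbital, 6 months | Same sites, 3 months | Not named in either |
| Non-ablative laser or light, microdermabrasion, superficial peels | No site limit, 3 months | No site limit, 3 months | Yes, both |
| Medium-depth to deep peels | Any facial site, 6 months | Any facial site, 3 months | Yes, both |
| Botulinum toxin | Any use (exclusion 4) | Any use | Yes, both |
| Brow lift, eyebrow surgery | Ever (exclusion 9) | Not listed | Yes, at entry |

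The gap is therefore the first three rows. For laser it concerns only resurfacing that is not non-ablative. Two further mismatches appear: Section 7.5 omits the whole content of exclusion 10, and the look-back for deeper peels and laser resurfacing is 6 months in one list and 3 months in the other.

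**Other provisions that might close the gap.** Inclusion 4 requires moderate to severe lines before treatment. Exclusions 11 to 14 deal with asymmetry and scarring, fixed lines, permanent make-up and skin-care regimen. None of them bars a glabellar filler, implant, graft or resurfacing as such. Section 5.4.1 lets a subject be terminated for newly meeting an exclusion. That partly makes up for the missing Section 7.5 bullet in the mid-face and periorbital areas, but not in the glabella, because exclusion 10 does not name it.

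**Leverage of one affected subject.** Inputs: 5 active and 1 placebo subject per cohort (Section 10.5); placebo pooled across cohorts (Section 10.2), so 7 subjects with seven cohorts and 9 with nine; FWS graded 0 to 3. The shift in one subject's score is an assumption.

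Change in group mean = shift / n.

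| Group | n | 1-grade shift | 2-grade shift |
|---|---|---|---|
| One dose cohort | 5 | 1/5 = 0.20 | 2/5 = 0.40 |
| Pooled placebo, 7 cohorts | 7 | 1/7 = 0.14 | 2/7 = 0.29 |
| Pooled placebo, 9 cohorts | 9 | 1/9 = 0.11 | 2/9 = 0.22 |

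**Which shifts are possible.** An eligible baseline is 2 or 3. Filler wearing off can move a 2 to a 3, which is 1 grade, and cannot move a 3 at all. A 2-grade shift would need a procedure during the study.

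**The case against.** A reader might infer that any recent cosmetic treatment of the glabella is open to subjects. The documents do not support that: the last four rows of the first table are covered at entry without a mid-face or periorbital limit. Nor is all laser treatment unrestricted, since the non-ablative item has no site limit in either list.

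Four further arguments deserve weight.

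- *Periorbital* is undefined. Exclusion 9 groups periorbital surgery with brow procedures, and the lateral corrugator injections are located relative to the supraorbital ridge, so a site could read the term as reaching the brow. That is possible, but the text does not settle it, and the two sites planned in Section 5.3 could differ.
- Section 7.4 lists the concomitant medications and treatments that are allowed, and filler is not among them. Hence it goes too far to say that on-study filler could never be treated as a breach. However, the duty to notify the sponsor is worded for medications and does not clearly reach a procedure.
- The endpoint is summarized as change from baseline (Section 10.4.2), so a stable earlier filler largely cancels. This stands. What remains is filler still resorbing and anything placed after dosing.
- All analyses are descriptive (Section 10.2), so no formal test is distorted. This also stands, but the dose-group summaries are then the efficacy result itself.

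**Conclusion.** The point holds in a limited form. On a literal reading, glabellar filler (temporary or permanent), implant, fat graft, or laser resurfacing other than non-ablative neither clearly excludes a subject nor is listed as prohibited on study. Section 7.5 also leaves out permanent fillers, implants and fat altogether.

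One affected subject with a 1-grade shift moves a dose mean by 0.20 and a pooled placebo mean by 0.14 (0.11 with nine cohorts). The figures of 0.40, 0.29 and 0.22 apply only to a 2-grade shift. The shift is assumed, and the documents give no basis for how many subjects would be affected, so these figures show leverage and not expected bias. Because the gap concerns the very area being scored, groups are small and the correction is cheap, the wording should be changed.

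**What to change.** 1. Add *glabellar* to the area-limited items: the temporary-filler and laser-resurfacing bullets of exclusion 8, exclusion 10, the same items in the synopsis, and the matching bullets of Section 7.5. Extending the list to the forehead is not needed on this argument, because the endpoint scores glabellar lines only.
2. Add permanent fillers, implants and autologous fat to the Section 7.5 list.
3. Reconcile the look-back for medium-depth to deep peels and laser resurfacing, which is 6 months in exclusion 8 and 3 months in Section 7.5. The sponsor should decide which period is meant and state it once.

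The cost is a few words in an amendment and no added procedure. A few candidates with earlier glabellar procedures would become ineligible.
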